4.3.2. Study Days and Visit Windows

Study days are numbered relative to the first day of IMP administration. The start of treatment (Day 1) is defined as the date on which a patient takes the first dose of IMP. Days will be numbered relative to treatment start (ie, ..., -2, -1, 1, 2, ...; with day 1 being the first day of IMP administration and day -1 being the day before the first day of IMP drug administration).

For data collected at the investigational center visits, such as RV (TV1), TV2 to TV6/IMP DV, efficacy and safety data will be analyzed using the visit recorded in the case report forms (CRFs) unless otherwise stated for by-visit summaries. If there are multiple assessments at a postbaseline visit, then the last nonmissing assessment at that visit will be used for the summary. This includes assessments at scheduled and unscheduled visits (the reason for the unscheduled visit has to be included for that particular assessment). If there are both scheduled and unscheduled visits with nonmissing results at the specific visit, the last nonmissing assessment will be used for the summary. For the purpose of the efficacy analysis, assessments collected at the

unscheduled early termination visit will be assigned to the next scheduled visit and also used as the final assessment for the final assessment summaries.

For the analysis of electronic patient diary recorded data (ie, pulmonary function test [PFT], rescue medication usage and asthma symptom score, etc.), the day used for analysis consists of the evening assessment for the date of the first dose of IMP and the morning assessment for the following day as illustrated in [Table 4](#).

Weekly average data will be generated using 7-day windows based on study days (before and after the first dose of double-blind IMP). For example, week 6 will start from day 36 to day 42. A summary will be provided using the derived week window.

Table 4: Analysis Day

Analysis day	Study day	Time point
-1	1 (predose)	AM
1	1	PM
	2	AM
2	2	PM
	3	AM
X	X	PM
	X + 1	AM
84	84	PM
	85	AM

5. STUDY POPULATION

5.1. General

The ITT analysis set will be used for all study population summaries unless otherwise specified. Summaries will be presented by treatment group and for all patients.

5.2. Patient Disposition

The following data will be summarized using descriptive statistics: patients screened; patients screened but not enrolled (and reason); patients enrolled in the run-in period; patients enrolled in the run-in period but not randomized (and reason); patients randomized; patients randomized but not treated; ITT analysis set, patients in the ITT with retrieved data, ITT without retrieved data, safety, and PP analysis sets; patients who complete the treatment, and patients who withdraw from the treatment (and reason); patients who complete the study, and patients who withdraw from the study (and reason) will be summarized using counts and percentages. The summary will include all patients screened. The denominator for calculation of percentages will be the number of randomized patients. All disposition information for screened patients will be provided in a listing by patient.

5.3. Demographics and Baseline Characteristics

Demographics variables (age, age group [4-6 years, 7-11 years], ethnicity, race, sex, weight, height, and body mass index [BMI]) will be summarized using descriptive statistics (refer to section 4.1). Baseline characteristics (baseline percent predicted FEV₁, baseline PEF, and previous asthma therapy [ICS or NCS], etc.) will also be summarized using descriptive statistics.

Patient demographics will be presented for both ITT and Safety analysis sets. The PP analysis set will be presented if the difference between ITT and PP is more than 5 patients in any of the treatment arm.

A listing for demographics and baseline characteristics in the ITT analysis set will be presented.

Patient demographic and baseline characteristics, including medical history, and prior medications and therapies will be examined to assess the comparability of the treatment groups and will be summarized using descriptive statistics (refer to section 4.1). Categories for missing data will be presented if necessary.

5.4. Medical and Asthma History

All medical history will be coded using the Medical Dictionary for Regulatory Activities (MedDRA). The incidence of medical history abnormalities will be summarized using descriptive statistics by system organ class (SOC) and preferred term (PT). Patients are counted only once in each PT and SOC category. Patients who have a medical history assessment, with at least 1 abnormal finding and abnormal findings for each category will be summarized by treatment group and for all patients.

5.5. Prior Therapy and Medication

Any prior therapy and medication before study drug administration will be recorded on the CRF. Trade name or international nonproprietary name, indication, and dosage will be recorded. The sponsor will encode all therapy and medication according to the World Health Organization (WHO) drug dictionary (WHO Drug).

The incidence of prior therapies and medications will be summarized using descriptive statistics (count and percentages) by therapeutic class and PT. Patients are counted only once in each therapeutic class category, and only once in each preferred term category. Prior therapies and medications will include all medications taken and therapies administered before the first day of IMP administration.

5.6. Physical Examinations

Physical examinations, including height and weight, will be performed at the SV and at the final treatment visit (TV6/IMPDV). Patients with a physical examination, patients with at least 1 abnormal finding, and abnormal findings for each category will be summarized at baseline using descriptive statistics (counts and percentages). Abnormal values at or before screening will be reported as a part of medical history.

5.7. Childbearing Potential and Methods of Contraception

For all female patients, childbearing potential and premenarchal status will be listed.

5.8. Study Protocol Violations

Data from patients with any protocol violation (as recorded in protocol violation CRF) during the study will be summarized overall and for each category using descriptive statistics. Of note, medication errors, overdose, misuse, abuse, off-label use, and occupational exposure will be summarized in category "Non-Compliance to study medication".

Patient with at least 1 protocol violation for each category will be summarized using count and percentages.

6. EFFICACY ANALYSIS

6.1. General

The ITT analysis set will serve as the primary analysis set for all efficacy analyses, the PP population will serve as a supportive population for the primary efficacy analyses, as detailed below. Summaries will be presented by treatment group, unless specified otherwise.

Descriptive statistics (n, mean, SD, SE, median, min, and max) for efficacy variables and change from baseline will be provided by visit or week window, as appropriate. Final assessments will compare between treatment groups.

6.2. Primary Estimands and Efficacy Analyses

The estimands selected for the 2 primary endpoints will assess the change from baseline due to the initially randomized treatment as actually taken. These estimands assess the effectiveness at week 12, focusing on the causal effects attributable to the initially randomized medication. The sponsor will make all efforts to avoid study withdrawal in this 12-week study. In instances where a patient decides to discontinue IMP or, more importantly, requires alternative therapy for worsening asthma or an asthma exacerbation, the investigators will be instructed to encourage the patient to continue in the study and return for planned visits until the study completion in order to collect data after IMP discontinuation.

The question of whether to use data collected after IMP discontinuation is an ongoing debate in statistical literature, in particular for studies with symptomatic endpoints and when it is common for patients who dropout to switch therapies ([Mallinckrodt et al 2016](#), [Mallinckrodt 2013](#), [Little and Kang 2015](#), [O'Neill and Temple 2012](#)). This study is designed as a placebo-controlled study and it is expected that patients randomized to placebo would discontinue IMP due to worsening asthma at a higher rate than those randomized to active treatment, which is known to be an efficacious drug as established by multiple studies. After a patient discontinues IMP due to worsening asthma, the patient will be placed on alternative asthma therapies. The first choice will be ICS or a combination of ICS/LABA, exactly the classes of drugs being studied. Other therapeutic choices will include systemic corticosteroids, additional medications other than ICS, or both. All alternatives are proven to alter the spirometry collected after that point and therefore not be appropriate for assessment of IMP effectiveness. Improvement of asthma would be expected as rapidly and early as 1 week for FEV₁ for placebo patients placed on ICS ([Szeffler et al 1999](#)). It has also been shown that patients placed on ICS with long acting beta-agonists can have significant improvement in serial FEV₁ measurements on the same day ([Corren et al 2007](#), [Pearlman et al 1999](#)). Therefore, any patient who discontinued IMP and was placed on alternative therapies would be expected to have rapid and demonstrable improvements in lung function approximating the levels measured at screening.

The inclusion of patients who failed therapy and who were then treated with alternative medication would blunt the treatment effect, potentially causing the study to fail due to the analysis rather than the effectiveness of the treatment given during the study. These patients no longer represent a true placebo population and including them in the population for the primary outcome is not consistent with treatment by placebo. As a matter of fact, if retrieved drop outs

placed on the alternative therapy such as ICS or ICS/LABA treatments, the efficacy would be compared between two identical classes of drugs, making such comparison not appropriate for the clinical trial designed and powered as the placebo-controlled trial.

In a study recently completed by Teva under IND 114865, Study BDB-AS-30039, patients randomized to placebo had indeed higher IMP discontinuation rates than patients randomized to either of the 3 active treatment arms with beclomethasone dipropionate breath-actuated inhaler (BAI). Study BDB-AS-30039 was a randomized, double-blind, placebo-controlled, parallel-group trial that investigated the use of beclomethasone dipropionate BAI in patients 12 years of age and older with persistent asthma. Data from this study indicated that patients receiving placebo placed on alternative asthma therapies after IMP discontinuation had marked improvements in spirometry results collected after that IMP discontinuation (Table 5). Study BDB-AS-30039 had a shorter duration (6 weeks) than FSS-AS-30003 (12 weeks) and included adults, but patients were encouraged to attend study visits after discontinuation of IMP.

The study had 4 arms: placebo and 3 active treatment arms. IMP discontinuation rates were

11.2% in the placebo treatment arm compared to 3.1% in the pooled active treatment arm; 10 of the patients treated with placebo (9.3%) withdrew due to worsening asthma, while only 2 patients combined from all 3 active groups withdrew due to worsening asthma (0.6%). Table 5 shows the data collected for each individual patient after resumption of alternative therapy resulted in large increases from baseline for placebo.

Table 5: Standardized Baseline-adjusted Trough Morning FEV₁ Area Under the Effect Curve from Time Zero to 6 Weeks for Individual Patient who Discontinued IMP with Retrieve Dropout Data

Based upon the experiences with Study BDB-AS-30039 and Study BDB-AS-302, Teva is concerned that an imbalance in treatment discontinuation rates coupled with a markedly reduced treatment effect as a result of alternative asthma therapies for patients randomized to placebo will likely result in a study that fails to show a statistically significant effect of investigational therapy. In light of these issues, retrieved dropout data will be used only for sensitivity analyses. Missing data for patients who discontinue IMP will be imputed using reference-based multiple imputations representing a missing not at random (MNAR) mechanism. This approach is discussed [Mallinckrodt et al 2016](#) (sections 3.2 and 3.4 for estimand 2 in the paper).

6.2.1. Variable Definition

A handheld device to measure FEV₁ will be provided to patients at the SV and used to determine the percent predicted trough morning FEV₁ throughout the course of the study.

Weekly Average Percent Predicted Trough Morning FEV₁:

Baseline percent predicted trough morning FEV₁ is defined as the average value of recorded (nonmissing) morning assessments 5 out of the last 7 days prior to randomization (Section 4.2 for details). The first day before randomization consists of the electronic patient diary entry at **home** on the morning of the RV (TV1) and the first day postrandomization consists of electronic patient diary entry at **home** on the morning of the day after the RV (TV1).

For postdose weekly average of percent predicted trough morning FEV₁ measurements, the values will be the averages based on the available data for that week. The averages will be calculated as the sum of morning FEV₁ values divided by the number of nonmissing assessments. There will be no imputation applied to postrandomization assessments.

1-hour Postdose Percent Predicted Morning FEV₁ at Week 12:

The baseline predose FEV₁ should be performed at the **investigational center** between the hours of 0530 and 1100 using the handheld device before administration of study drug or rescue medications (Section 4.2 for details).

The IMP dose should be administered right after the predose FEV₁ measurement (eg, within a 10-minute window). The patient will then perform 1-hour (+/-10 minutes) postdose lung function assessments on week 12 at the **investigational center**.

Electronic patient diary percent predicted FEV₁ time will be compared with IMP dose time. If a percent predicted FEV₁ measurement is performed after the IMP dose, a 10-minute window will be allowed and that measurement will be included in the analysis, otherwise the percent predicted FEV₁ measurement will be ignored.

Patients who have been withdrawn from IMP will be asked to perform 1-hour postdose lung function assessments; although the patients will not be taking a dose of IMP, the assessment should be performed approximately 1 hour after the predose lung function assessments were obtained.

6.2.2. Primary Efficacy Analysis

6.2.2.1. For Fp MDPI versus Placebo: Change from Baseline in Weekly Average of the Percent Predicted Trough Morning FEV₁ at Week 12

For the purpose of the efficacy analysis of weekly average of daily morning FEV₁ measurements, the FEV₁ value at week 12 will be the average based on the available data for that week. The averages will be calculated as the sum of the morning FEV₁ values divided by the number of nonmissing assessments. There will be no imputation applied to postrandomization daily assessments.

The primary analysis of the change from baseline in weekly average of percent predicted morning FEV₁ at week 12 due to the initially randomized treatment as actually taken will be analyzed using an ANCOVA model with effects due to baseline percent predicted trough

morning FEV₁, sex, age, (pooled) investigational center, previous therapy (ICS or NCS), and IMP treatment group. Contrasts for pairwise treatment comparisons of interest will be constructed. The estimated treatment difference between each IMP treatment group and the placebo group will be presented together with the 2-sided 95% CI for the difference and the p-value.

In this analysis, missing data that are caused by early dropouts from the study or from IMP (regardless of availability of retrieved dropout data) will be imputed using reference-based multiple imputations which represents a missing not at random (MNAR) mechanism. The reference-based multiple imputation method multiply imputes the missing data in treatment group based on an imputation model built using data from the placebo group. This will yield a conservative treatment effect estimate as compared to the estimate obtained from multiple imputations (MI) under a missing at random (MAR) mechanism. The methodology and algorithm used for imputation is described in [Appendix A](#).

6.2.2.2. For FS MDPI versus Fp MDPI: Change from Baseline in 1-hour Postdose Percent Predicted Morning FEV₁ at Week 12

The baseline predose percent predicted trough morning FEV₁ will be performed at the **investigational center** at the RV (TV1) (Section 4.2 for details). The postdose percent predicted morning FEV₁ (measured at the investigational center) at week 12 with the handheld device will be approximately 1-hour after the IMP administration.

The co-primary endpoint change from baseline in 1-hour postdose percent predicted morning FEV₁ at week 12 will be analyzed using an ANCOVA model with effects due to baseline trough morning percent predicted FEV₁, sex, age, (pooled) investigational center, previous therapy (ICS or NCS), and IMP treatment group. Contrasts for pairwise treatment comparisons of interest will be constructed. The estimated treatment comparisons of interest will be presented together with the 2-sided 95% CI for the difference and the p-value. Missing 1-hour postdose FEV₁ data at week 12 will be handled similarly to the above (see [Appendix A](#) for details).

For patients who completed the treatment period, but with clinically and physiologically implausible data (eg, percent predicted FEV₁ values post-randomization is $\geq 200\%$), imputation will be based on measurements observed at previous weeks and in the same treatment group (this represent a MAR mechanism).

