At each visit, the investigational center staff will determine if patients have experienced any adverse events, changes in medical history, changes in medication, or any difficulty following study procedures. The C-ACT will be completed by the patient and the patient's parent/legal guardian/caregiver (as applicable) at the investigational center, before any other assessments are performed, at specified visits. The same parent/legal guardian/caregiver should complete the assessments at each visit, if possible.

A telephone call may be conducted as needed during the alternate, non-visit weeks (weeks 5, 7, etc) to monitor the patients' safety and to assess their asthma status or for any other relevant reason.

At the end of the study, a FV (which may be a follow-up investigational center visit or telephone call) will be conducted 7±2 days after TV6 (week 12) to monitor safety of the patients.

Patients who meet the alert criteria for worsening asthma as defined for this study or experience worsening of asthma including asthma exacerbation will present to the investigational center for an investigator assessment as soon as possible. If possible and when it is judged safe to do so, this visit should be conducted before a change in asthma therapy takes place. Following investigator assessment of the patient's asthma status a decision will be made whether or not it is safe for a patient to continue the IMP. In cases where the IMP is to be withdrawn and alternative therapy started, the investigational center staff should contact the medical monitor to confirm the findings. In the event that it is considered in the best interest of a patient to stop the IMP and initiate an alternative asthma therapy, the patient will undergo all visit procedures required for the IMPDV. After the IMPDV, IMP dosing will not occur. The investigator should discuss and implement alternative asthma treatment that is appropriate for the patient. These patients will

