continue to participate in all study visits as scheduled and continue to complete all morning and evening study procedures except for the IMP dosing. Patients will be asked to perform 1-hour postdose lung function assessments at the remaining treatment visits; although the patients will not be taking a dose of IMP, the assessment should be approximately 1 hour after the predose lung function assessments were obtained. If a patient or patient's parent/legal guardian/caregiver elects to completely withdraw from the study (ie, withdraw consent) prior to the investigator assessment or investigational center visit, irrespective of the reason for the study discontinuation, every attempt will be made to conduct the IMPDV subsequent to the patient's withdrawal from the IMP.

Asthma exacerbation that requires a change in medication or worsening of asthma that requires the patient to be treated with alternative therapy will be entered into the case report form (CRF), including the date at which any medication change was made and whether this medication change was implemented prior to or after the IMPDV lung function assessments (FEV₁ and PEF) were completed. Asthma worsening including asthma exacerbations with a change to alternative asthma therapy will not be considered an adverse event for this study since it is an expected outcome for this study in an asthmatic patient population. Asthma exacerbations that meet the criteria for a serious adverse event will be recorded as adverse events.

At TV6 (week 12), or the IMPDV as applicable, the investigator will discuss asthma treatment with the patient after safety assessments have been completed, and any medication started for the purpose of newly recommended asthma treatment will not be considered a protocol violation. This asthma therapy will be recorded in the CRF following IMP discontinuation (planned or unplanned). Additionally, an investigational center visit may be conducted at any time at the request of the patient or parent/legal guardian/caregiver, as applicable or at the discretion of the investigator.

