2.4. Sample Size and Power Considerations

Sample size and power calculations are driven by demonstrating superiority of FS MDPI 50/12.5 mcg twice daily over Fp MDPI 50 mcg twice daily in change from baseline in 1-hour postdose percent predicted morning FEV₁ at week 12 and the superiority of Fp MDPI 50 mcg twice daily over placebo in change from baseline in percent predicted trough morning FEV₁ at week 12.

For the superiority comparison of FS MDPI 50/12.5 mcg twice daily versus Fp MDPI 50 mcg twice daily, assuming that the change from baseline in 1-hour postdose percent predicted morning FEV₁ at week 12 is analyzed using an ANOVA model with only a single factor of treatment group, the following assumptions were made:

- The initial assumed common standard deviation (SD) was 9.3% and the true treatment difference was 4.5% between FS MDPI 50/12.5 mcg twice daily and Fp MDPI 50 mcg twice daily. This assumption was based on data collected in previous Teva studies with the same Fp MDPI and FS MDPI products in adult asthma patients who completed the 12-week treatment period and based on office-based spirometry.
- The initial power was 97% at a 2-sided significance level of 5%.

For the superiority comparison of Fp MDPI 50 mcg twice daily versus placebo, assuming that the change from baseline in percent predicted trough morning FEV₁ at week 12 is analyzed using an analysis of variance (ANOVA) model with only a single factor of treatment group, the following assumptions were made:

- The initial assumed common standard deviation (SD) was 13.25% and the true treatment difference was 5% between Fp MDPI 50 mcg twice daily and placebo. This assumption was based on data collected in previous Teva studies with the same Fp MDPI product in adult asthma patients and based on office-based spirometry
- The initial power was 85% at a 2-sided significance level of 5%.

Study FSS-AS-30003 is the very first study in which a handheld spirometry device is utilized 1) as the primary endpoint in a Phase 3 study and 2) in a pediatric asthma patient population for a pivotal study of this scale. This made it difficult to predict the actual variability of the data. A blinded sample size reassessment was not planned. Routine blinded data monitoring of this study FSS-AS-30003 revealed that the SD for the overall study population is indeed higher than the initial assumptions. In addition, FEV₁ stability has been monitored closely throughout this study

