6.3.1.5. Time to First Onset of Effect

Patients will record the number of inhalations of rescue medication (albuterol/salbutamol HFA MDI [90 mcg ex-actuator] or equivalent) each morning and evening in the electronic patient diary. Total daily use will be calculated after the RV. The time to first onset of effect is defined as the first decrease from the weekly average baseline in daily rescue medication use.

6.3.1.6. Proportion of Patients Discontinued From IMP for Asthma Exacerbation During the 12-week Treatment Period

Once the investigator confirms that a case of asthma exacerbation requiring a significant alternative treatment has occurred, the event will be entered into the CRF as an asthma exacerbation event. Such patients will be discontinued from IMP. The proportion of patients discontinued from IMP for asthma exacerbation during the 12-week treatment period will be assessed.

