8.6. Asthma Exacerbations

Asthma exacerbations that requires a change in medication or worsening of asthma that requires the patient to be treated with alternative therapy will be entered into the case report form (CRF), including the date at which any medication change was made and whether this medication change was implemented prior to or after the IMPDV lung function assessments (FEV₁ and PEF) were completed. Asthma worsening including asthma exacerbations with a change to alternative asthma therapy will not be considered an adverse event for this study since it is an expected outcome for this study in an asthmatic patient population. Asthma exacerbations that meet the criteria for a serious adverse event will be recorded as adverse events. For the purpose of this study, an asthma exacerbation is defined as worsening of asthma requiring any significant treatment other than IMP and study rescue medication.

The number and percentage (%) of patients experiencing an asthma exacerbation will be presented by treatment group.

A summary of the number and percentage of patients with asthma exacerbations resulting in hospitalization, leading to permanent withdrawal of study drug, and other actions will be presented by treatment group.

The number and percentage of patients with asthma exacerbations will be presented by maximum severity and treatment group. Severity will be classified as "mild", "moderate", or "severe". If a patient experiences more than 1 asthma exacerbations, only the asthma exacerbations with the greatest severity will be included in the summary table.

In all of the above summaries, each patient will be counted only once regardless of the number of asthma exacerbations experienced during the study.

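### The primary analysis ends usable FEV1 data when IMP stops, although its stated reason is the start of alternative asthma therapy; values taken between the two count as on-treatment

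*SAP*

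**What the plan says.** **Rationale.** SAP 6.2 argues that counting children who failed and were then "treated with alternative medication would blunt the treatment effect". It expects FEV1 to recover quickly once such therapy begins.

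**Operative cut.** For the trough endpoint, SAP 6.2.2.1 states that "missing data that are caused by early dropouts from the study or from IMP (regardless of availability of retrieved dropout data) will be imputed". SAP 6.2.2.2 and Appendix A apply the same approach to the 1-hour endpoint. SAP 4.1 defines retrieved dropout data as data collected after IMP discontinuation.

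**Timing of the therapy change.** Under Protocol 3.1, a child with worsening asthma attends for assessment, before any therapy change if that is possible and judged safe. The CRF captures the date of the change and "whether this medication change was implemented prior to or after the IMPDV lung function assessments". SAP 8.6 repeats that this is collected.

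**Visit mapping.** SAP 4.3.2 assigns efficacy assessments from an unscheduled early termination visit to the next scheduled visit. Protocol Table 3 includes a 1-hour FEV1 at the IMPDV.

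**IMP after an exacerbation.** Protocol 3.1 says that after assessment of worsening, including exacerbation, "a decision will be made whether or not it is safe for a patient to continue the IMP". Protocol 3.1 and 4.3.1 also say IMP is stopped when blinded management is not safely possible because the asthma warrants a treatment change. SAP 6.3.1.6 says of children with a confirmed exacerbation needing significant alternative treatment: "Such patients will be discontinued from IMP". SAP 8.6 plans a summary of exacerbations resulting in hospitalization, "leading to permanent withdrawal of study drug, and other actions will be presented by treatment group".

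**The concern.** The reason for excluding data and the event that triggers the exclusion are different. The reason is exposure to alternative therapy. The trigger is leaving IMP or the study. If both always fell on the same day this would not matter, but the CRF item exists because the order can vary. Any FEV1 measured between the two dates is of the kind SAP 6.2 calls unsuitable for judging IMP, yet it enters as an ordinary on-treatment observation.

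At stake is whether the primary analysis delivers the estimand the SAP argues for. The sponsor expects placebo children to worsen and need other therapy more often, so unflagged values would fall mainly in the placebo arm.

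**Working it through.** **Step 1. Does any rule use the therapy-change date?** The places where usable data are defined are SAP 4.1 (retrieved dropout), 4.3.1 (missing data), 6.2.2.1, 6.2.2.2 and Appendix A. Each refers to dropout from the study or from IMP, or to completers with implausible values. None refers to the start of alternative therapy or to the before/after-IMPDV item.

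**Step 2. How can such a value reach a primary endpoint?** Call the start of alternative therapy A and the last IMP dose B, with A before B.

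- *B falls before week 12, trough endpoint.* Week 12 is imputed under Appendix A. Weekly averages between A and B enter only as predictors in the imputation model.
- *The child is still on IMP in week 12.* SAP 4.3.2 puts week 6 at days 36 to 42, so week k runs from day 7(k − 1) + 1 to day 7k, and week 12 is days 78 to 84. Values after A in that window are averaged as observed. If the child is also on IMP at TV6, the 1-hour value counts as observed too.
- *B falls between TV5 (week 8) and TV6, 1-hour endpoint.* If the early-termination mapping covers the IMPDV, the next scheduled visit is week 12. A post-switch IMPDV value could then stand as the week-12 observation instead of being imputed. SAP 4.3.2 does not say whether the IMPDV is covered, or which rule wins over Appendix A.

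**Step 3. Scale.** SAP 2.4 assumed initially that "the true treatment difference was 5% between Fp MDPI 50 mcg twice daily and placebo". With the revised SD of 17 and 80% power, using 5 as the treatment difference:

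n per group = 2 × (1.960 + 0.842)² × 17² / 5² = 2 × 7.85 × 289 / 25 ≈ 181.5.

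This agrees with the planned 181 within rounding, so 5 points is a fair yardstick.

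Let f_P and f_A be the shares of placebo and active children whose week-12 value is post-switch but counted as observed, and g their mean gain in percent predicted FEV1. The Fp-placebo difference shrinks by

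L = (f_P − f_A) × g.

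The documents give none of these three quantities. Purely as assumptions, f_P − f_A of 1% to 5% and g of 5 to 10 points give L from 0.01 × 5 = 0.05 to 0.05 × 10 = 0.50 points, or 1% to 10% of the assumed 5. This shows how the loss scales; it does not estimate it.

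**Step 4. The passages on continuing IMP, side by side.** Protocol 3.1 leaves continuation to a decision even where there is an exacerbation, which by definition requires significant added treatment. SAP 8.6 lists other actions beside permanent withdrawal. Against these, Protocol 3.1 and 4.3.1 stop IMP where the asthma warrants a treatment change and blinded management is not safe, and SAP 6.3.1.6 says IMP is discontinued. How often A occurs with no B before week 12 depends on which passage sites follow.

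**The case against.** The strongest reply is that the protocol largely pairs the two events. It presents a choice between blinded management and a change of therapy, speaks of withdrawing IMP and starting alternative therapy together, and prohibits other ICS, LABA, leukotriene modifiers and systemic corticosteroids (5.7, Appendix H). The CRF item presupposes an IMPDV, so IMP does stop in those cases. The other actions in SAP 8.6 are undefined and need not mean continued IMP. This stands to a large extent: a reader might infer that the protocol permits alternative therapy without stopping IMP, but no passage says so. What the documents show is a conflict of wording. They do not show that the interval between the two dates is always empty, and the SAP has no rule for it.

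Second, children who stop IMP before week 12 are imputed anyway, so the trough endpoint is barely touched by this route. That stands.

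Third, the per-protocol set drops violations that could affect the primary outcome, and the completer analysis drops major violators. Prohibited-medication use may qualify under Protocol Appendix C. Both are supportive analyses only.

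Fourth, a permanent cut at first alternative medication would discard later on-IMP values in any child who had a short early course and continued IMP. It also requires the estimand text to name the second event. Both are true and belong in the cost.

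**Conclusion.** The gap is real and narrow. The primary cut should follow the event that SAP 6.2 gives as its reason, and at present it does not. Direct effect on a primary endpoint needs a child still on IMP in week 12 after switching, or a post-switch IMPDV 1-hour value carried to week 12. The size cannot be derived from the documents and is probably small. For Fp versus placebo the likely bias is toward no difference, assuming placebo children switch more often and improve when they do. For FS versus Fp 50 no direction can be derived; Protocol 1.3.1.2 reports similar exacerbation frequency in those groups in two earlier studies.

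Two further inferences are not supported:

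- *A power loss built on the 9.3% placebo and 0.6% active rates in SAP 6.2.* Those patients did withdraw for worsening asthma, and equivalent children here would be imputed. The rates come from a 6-week study of a different drug in patients aged 12 and older. No document gives a rate of switching with IMP continued, or the resulting FEV1 gain.
- *That the secondary endpoint on IMP discontinuation for exacerbation is defective.* It measures what its name says. A child who switches first and then stops IMP for the exacerbation is still counted, and SAP 8.6 already summarizes all exacerbations by arm.

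**What to change.** Before unblinding, amend the SAP as follows:

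1. In 4.1, 6.2.2 and Appendix A, end usable primary-analysis data at the earlier of the last IMP dose and the CRF-recorded start date of alternative asthma medication. Name both events in the estimand text in 6.2.
2. Impute after that point exactly as for IMP discontinuers.
3. Widen the retrieved-dropout definition so that the removed values enter the existing sensitivity analysis with retrieved data.
4. In 4.3.2, state that IMPDV values taken after a therapy change are not mapped to week 12 in the primary analysis, using the before/after item already in the CRF.
5. Reconcile Protocol 3.1 and 4.3.1 with SAP 6.3.1.6 and 8.6 on what happens to IMP after an exacerbation. Which rule is right is a clinical matter for the sponsor.

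The cost is SAP text and one derived date, with no new data collection. Slightly more values are imputed, including later on-IMP values in any child who received alternative medication and continued IMP. Reporting the number of children and values removed by the new date, by arm, would show how much the change matters.
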